14.1 Cohort A and Cohort C– Brain Metastases

For subjects with BM (Cohorts A and C) efficacy will be evaluated by RECIST 1.1 criteria separately for non-CNS tumor lesions and for BMs at screening, Cycle 2 Day 1, Cycle 3 Day 1, and then every 2 cycles (approximately 8 weeks) thereafter until disease progression.

14.2 Cohort B – Leptomeningeal Metastases

For subjects with LM, symptoms attributed to leptomeningeal metastases will be evaluated at screening, Cycle 1 Day 1, Cycle 1 Day 14, Cycle 2 Day 1, Cycle 3 Day 1, and then every 2 cycles (approximately 8 weeks) thereafter until disease progression, as well as at the End of Drug Treatment visit. CTCAE v4.03

(www.hrc.govt.nz/sites/default/files/CTCAE%20manual%20-%20DMCC.pdf) will be utilized for the evaluation of symptoms and signs attributed to leptomeningeal metastases. Symptom improvement is defined as a decrease in 1 grade in at least one CTCAE v4.03 symptom or sign attributed to leptomeningeal metastases without worsening of other neurologic symptoms or signs attributed to leptomeningeal metastases. Symptom progression is defined as an increase of 1 grade in at least one CTCAE v4.03 symptom attributed to leptomeningeal metastases or the appearance of new symptoms or signs of LM. Symptoms or signs attributed to leptomeningeal metastases will be followed as one component of the efficacy evaluation for Cohort B.

For subjects with LM, NSCLC cells in the CSF will be evaluated during the study (screening, Day 14 of Cycle 1, and on Day 1 of Cycle 3) for malignant cells both by standard cytological analysis and by a rare cell detection methodology. CSF obtained at the same time points will be evaluated for protein and glucose levels. Response will be based on standard cytological analysis if cytology was positive at screening. Response categories will be CR (no malignant cells, which must be present on 2 consecutive CSF evaluations to support response of CR), and non-PR, non-PD (continued presence of malignant cells). PD will not be defined by CSF cytology.

For subjects with LM (Cohort B), CSF for isolation of cell-free DNA will be collected at screening, Day 14 of Cycle 1, and Day 1 of Cycle 3. Evaluation for EGFR mutations will be performed. Quantitation of EGFR mutations in cell-free DNA will be utilized for an exploratory efficacy analysis.

LM will also be evaluated by serial MRI of the brain. For patients with positive findings of LM on MRI at screening, response categories will be CR (no evidence of LM on MRI), or non-PR, non-PD (continued presence of evidence of LM on MRI). PD for LM will not be defined by MRI.

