8.4 Inclusion Criteria – Cohort B

A subject must meet the following criteria to be eligible for entry into the study:

1. Age \geq 18 years old.
2. History of NSCLC with EGFR mutation (either exon 19 deletion or L858R mutation or of an EGFR mutation that has had a clinical response to erlotinib, afatinib, or gefitinib in the patient being enrolled).
3. Presentation with LM at initial presentation with no prior systemic treatment, or occurrence or progression of LM while receiving first line therapy (either erlotinib or afatinib or gefitinib) for at least 14 days. Patients may have received osimertinib (or other agents inhibiting the T790M EGFR mutation) as second line therapy. If LM progression occurs after osimertinib, patient will be eligible.
4. Presence of at least one CTCAE 4.03 symptom or sign of at least Grade 1 attributed to leptomeningeal metastases.
5. Diagnosis of LM by:
 - a) Cytological evidence in CSF sample of LM due to NSCLC, and/or
 - b) Findings on gadolinium-enhanced MRI
6. No clinically significant progression outside of the CNS on most recent EGFR inhibitor therapy.
7. Concomitant brain metastases and brain metastases previously treated with radiation therapy are allowed. (Subjects with symptoms or signs attributed to LM will be enrolled in Cohort B whether or not they have brain metastases.)

-
8. ECOG Score ≤ 2 .
 9. No history of another malignancy in the 5 years prior to study entry, except treated non-melanoma skin cancer or superficial bladder cancer or carcinoma-in-situ of the cervix or Stage 1 or 2 cancers of other sites that have been treated surgically and have not recurred.
 10. Adequate organ and bone marrow functions as follows:
 - a) Serum creatinine ≤ 1.5 mg/dL
 - b) Total bilirubin $\leq 1.5 \times$ ULN (except in patients diagnosed with Gilbert's disease where bilirubin must be $\leq 3 \times$ ULN).
 - c) ALT and AST $\leq 3 \times$ ULN
 - d) WBC $> 3000/\text{mm}^3$
 - e) Absolute neutrophil count $\geq 1500/\text{mm}^3$
 - f) Platelet count $> 100,000/\text{mm}^3$
 - g) Hemoglobin > 8 g/dL
 11. Serum potassium and magnesium levels above the LLN.
 12. No coexisting medical problems of sufficient severity to limit compliance with the study.
 13. Willing and able to sign written informed consent and be able to comply with the study protocol for the duration of the study.

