16.2 Sample Size Justification

For Cohort A, assuming that 20% of subjects with BM have RECIST 1.1 response (CR or PR), the study has an approximately 80% chance of having at least 3 subjects with RECIST 1.1 response, and an over 90% chance of at least 2 subjects having a response. All subjects who take at least one dose of study drug will be evaluable for safety and efficacy assessments.

For Cohort B, assuming that 20% of subjects with LM have improvement in at least one symptom or sign attributed to leptomeningeal metastases, the study has an approximately 80% chance of having at least 3 subjects with improvement in at least one symptom or sign attributed to leptomeningeal metastases and an over 90% chance of at least 2 subjects having improvement attributed to leptomeningeal metastases. All subjects who take at least one dose of study drug will be evaluable for safety and efficacy assessments.

For Cohort C, assuming that 20% of subjects with BM have RECIST 1.1 response (CR or PR), the study has an approximately 80% chance of having at least 3 subjects with RECIST 1.1 response, and an over 90% chance of at least 2 subjects having a response. All subjects who take at least one dose of study drug will be evaluable for safety and efficacy assessments.

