Complete Response (CR): Disappearance of all non-target lesions and normalization of tumor marker level. All lymph nodes must be non-pathological in size (< 10 mm short axis).

Note: If tumor markers are initially above the upper normal limit, they must normalize for a subject to be considered in complete clinical response.

Non-CR/Non-PD: Persistence of 1 or more non-target lesion(s) and/or

maintenance of tumor marker level above the normal limits.

Progressive Disease (PD): Appearance of 1 or more new lesions and/or *unequivocal progression* of existing non-target lesions. *Unequivocal progression* should not normally trump target lesion status. It must be representative of overall disease status change, not a single lesion increase.

Although a clear progression of “non-target” lesions only is exceptional, the opinion of the treating physician should prevail in such circumstances, and the progression status should be confirmed at a later time by the review panel (or principal investigator).

Evaluation of Best Overall Response

The best overall response is the best response recorded from the start of the treatment until disease progression/recurrence (taking as reference for progressive disease the smallest measurements recorded since the treatment started). The subject's best response assignment will depend on the achievement of both measurement and confirmation criteria.

For Subjects with Measurable Disease (i.e., Target Disease)

Target Lesions	Non-Target Lesions	New Lesions	Overall Response	Best Overall Response when Confirmation is Required*
CR	CR	No	CR	≥ 4 wks. Confirmation**
CR	Non-CR/Non-PD	No	PR	
CR	Not evaluated	No	PR	
PR	Non-CR/Non-PD/not evaluated	No	PR	≥ 4 wks. Confirmation**
SD	Non-CR/Non-PD/not evaluated	No	SD	Documented at least once ≥ 4 wks. from Screening**
PD	Any	Yes or No	PD	No prior SD, PR or CR
Any	PD***	Yes or No	PD	
Any	Any	Yes	PD	

* See RECIST 1.1 manuscript for further details on what is evidence of a new lesion.

** Only for non-randomized trials with response as primary endpoint.

*** In exceptional circumstances, unequivocal progression in non-target lesions may be accepted as disease progression.

Note: Subjects with a global deterioration of health status requiring discontinuation of treatment without objective evidence of disease progression at that time should be reported as “*symptomatic deterioration.*” Every effort should be made to document the objective progression even after discontinuation of treatment.

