## 1.2.1 Sample Size Justification

For Cohort A, assuming that 20% of subjects with BM have response (complete response [CR] or partial response [PR]), N=20 has an approximately 80% chance of

having at least 3 subjects with response, and an over 90% chance of at least 2 subjects having a response.

For Cohort B, assuming that 20% of subjects with LM have improvement in at least one symptom or sign attributed to LM, N=20 has an approximately 80% chance of having at least 3 subjects with improvement in at least one symptom or sign attributed to leptomeningeal metastases and an over 90% chance of at least 2 subjects having improvement attributed to LM.

For Cohort C, assuming that 20% of subjects with BM have response (CR or PR), N=20 has an approximately 80% chance of having at least 3 subjects with response, and an over 90% chance of at least 2 subjects having a response.

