# 1.3 Efficacy Assessments

## 1.3.1 Efficacy Endpoints

## 1.3.1.1 Primary endpoints

Cohorts A and C: efficacy (changes in BM size) will be evaluated by RECIST 1.1 criteria separately for non-CNS tumor lesions and for BMs at screening, at Cycle 2 Day 1 (for BM), at Cycle 3 Day 1, and then every 2 cycles (approximately 8 weeks) thereafter until disease progression.

For Cohort B: symptoms and signs attributed to leptomeningeal disease will be evaluated at screening, Cycle 1 Day 1, at Cycle 1 Day 14, at Cycle 2 Day 1, at Cycle 3, and then every 2 cycles (approximately 8 weeks) thereafter until disease progression National Cancer Institute CTCAE (NCI CTCAE; Version 5). Symptom improvement is defined as a decrease in 1 grade in at least one CTCAE v4.03 symptom or sign attributed to LM without worsening of other symptoms or signs that are attributed to LM. Symptom progression is defined as an increase of 1 grade in at least one CTCAE v4.03 symptom or the appearance of new symptoms or signs of LM.

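### Cohort B's primary symptom response names no reference grading, no qualifying visits and no confirmation, so a transient one-grade dip can count and bias an uncontrolled rate upward

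*Protocol*

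**What the plan says.** Protocol 14.2 gives the primary endpoint of Cohort B: "Symptom improvement is defined as a decrease in 1 grade in at least one CTCAE v4.03 symptom or sign attributed to leptomeningeal metastases". The sentence goes on to require that other neurologic LM-attributed symptoms or signs have not worsened. SAP 1.3.1.1 repeats the rule ("Symptom improvement is defined as a decrease in 1 grade in at least one CTCAE v4.03 symptom or sign attributed to LM"), as does the synopsis; both drop the word neurologic from the no-worsening condition.

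The entry requirement in Protocol 8.4 is: "Presence of at least one CTCAE 4.03 symptom or sign of at least Grade 1 attributed to leptomeningeal metastases".

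Symptoms are graded at Screening, Cycle 1 Day 1, Cycle 1 Day 14, Cycle 2 Day 1 and Cycle 3 Day 1, then every 2 cycles until progression, and at the end-of-treatment visit (Protocol 14.2, Table 4-2). No passage says which grading is the reference, which visits count towards the rate, how long a decrease must last, or whether it must be seen again.

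Other responses differ. In Section 14, a cytology CR needs two consecutive clear CSF evaluations, while an LM CR on MRI has no repeat rule. Appendix A asks for confirmation at 4 weeks or more, footnoted "Only for non-randomized trials with response as primary endpoint", but that appendix is headed for non-CNS response.

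On size, Protocol 16.2 says: "For Cohort B, assuming that 20% of subjects with LM have improvement in at least one symptom or sign attributed to leptomeningeal metastases", there is an "approximately 80% chance of having at least 3 subjects with improvement in at least one symptom or sign" and "an over 90% chance of at least 2 subjects having improvement attributed to leptomeningeal metastases". SAP section 2 plans exact confidence intervals and no formal hypothesis testing.

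**The concern.** Subjects enter Cohort B because they have a symptom at that time, so some will grade better at a later visit whatever the drug does. For a subject with a single Grade 1 symptom, the no-worsening condition adds nothing at the visit of improvement: there is no other symptom to worsen unless a new one appears. One symptom-free clinic day then meets the definition, even if the symptom is back at the next visit. If Screening is the reference, relief before the first dose also counts.

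Two programmers could derive different primary rates from the same data, depending on the reference grading and visits they choose. The study is open-label and nonrandomized, and the investigator both grades the symptom and attributes it to LM. Without a control arm, the endpoint definition is the main protection against counting natural variation as activity.

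**Working it through.** **1. The plan's own figures.** Inputs: 20 subjects and an assumed rate of 20% (Protocol 16.2, SAP 1.2.1).

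- P(at least 3) = 1 − [0.8^20 + 20(0.2)(0.8^19) + 190(0.2²)(0.8^18)] = 1 − (0.0115 + 0.0576 + 0.1369) = 0.794
- P(at least 2) = 1 − (0.0115 + 0.0576) = 0.931

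Both stated figures are reproduced.

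**2. Number of post-dose gradings, k.** There are 3 by Cycle 3 Day 1, 4 by Cycle 5 Day 1, and 5 if the end-of-treatment visit follows.

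**3. Assumed input.** Let q be the chance per visit that a stable subject meets the full definition, no-worsening condition included. The documents do not give q; I use 3%, 5% and 10%.

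**4. Single-visit rule.**

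- Independent visits: 1 − (1 − q)^k. For q = 0.05, k = 3: 1 − 0.95³ = 0.143.
- Lag-1 correlation ρ = 0.5 (first-order Markov chain): 1 − (1 − q)[1 − q(1 − ρ)]^(k−1). For q = 0.10, k = 3: 1 − 0.9 × 0.95² = 0.188.

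**5. Decrease also present at the next visit.**

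- Independent, k = 3: 2q² − q³. For q = 0.10: 0.020 − 0.001 = 0.019.
- Correlated, k = 3: P11[q + (1 − q)P01], where P11 = q + ρ(1 − q) and P01 = q(1 − ρ). For q = 0.10: 0.55 × (0.10 + 0.9 × 0.05) = 0.080.
- For k = 4 and 5, the same probabilities are carried forward visit by visit.

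False-improvement rate, from k = 3 to k = 5:

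| q | Single visit, independent | Single visit, ρ = 0.5 | Confirmed, independent | Confirmed, ρ = 0.5 |
|---|---|---|---|---|
| 3% | 8.7–14.1% | 5.9–8.7% | 0.2–0.4% | 2.3–3.8% |
| 5% | 14.3–22.6% | 9.7–14.1% | 0.5–1.0% | 3.9–6.3% |
| 10% | 27.1–41.0% | 18.8–26.7% | 1.9–3.7% | 8.0–12.9% |

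**6. Does the no-worsening condition remove the problem?** Suppose each symptom has a 5% chance of falling a grade and a 5% chance of rising a grade at each visit. With two symptoms, q = 0.95² − 0.90² = 0.0925, which gives 1 − 0.9075³ = 25.3% over 3 visits, against 14.3% with one symptom. In this model a second symptom adds more chances to fall than the condition takes away.

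**7. What fluctuation alone would need to reach 20%.** Independent visits: q = 1 − 0.8^(1/k) = 7.2%, 5.4% or 4.4% for k = 3, 4 or 5. With ρ = 0.5: 10.7%, 8.7% or 7.3%.

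**The case against.** A reader might infer that fluctuation by itself yields the 20% rate. The documents do not support that as a fact: they contain no fluctuation rate, and at q = 3% none of the cases above reaches 20%. Early progression also limits the count. Gradings run only until progression, a one-grade rise is itself symptom progression, and five gradings need Cycle 5 Day 1 (4 × 28 = 112 days after the first dose) plus the end-of-treatment visit. With two gradings the rate at q = 3% is 1 − 0.97² = 5.9%.

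A reader might also infer that 3 of 20 is a success threshold that an inactive drug could pass. It is not. The 20% is a planning assumption, and the SAP rules out formal testing. Protocol section 16 has a general sentence on two-sided significance at 0.05, but no null rate is given for Cohort B.

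Nor does every other response in the protocol need repetition. In Section 14 only cytology CR does, and Section 14 states no confirmation for brain metastases. The case rests on the missing definition, not on Cohort B being singled out.

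It is fair to add that the SAP plans a by-visit response table and a listing of symptoms and signs by visit, so a transient dip would be visible. Cycle 1 Day 1 is the stated reference for steroid dose, tumor change and laboratory grade shifts, which makes it the natural default. Those points soften the concern but do not define the primary rate. That any single visit suffices is a reading of the documents' silence, not stated text; the silence is itself the defect.

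Finally, confirmation helps less when visits are correlated (up to 12.9% at q = 10%, against 3.7% if independent), and it does not remove persistent investigator or attribution bias.

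**Conclusion.** The point holds as a gap in the definition of a primary endpoint. The reference grading, the qualifying visits and any confirmation are unstated in Protocol 14.2, the synopsis and SAP 1.3.1.1. Followed as written, a Grade 1 symptom that disappears for one visit and returns can count as improvement, as can relief before the first dose if Screening is the reference.

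The consequence is upward bias in a single-arm rate. The exact interval does not reflect it, because that interval covers sampling error only: 4 of 20, for example, gives 5.7% to 43.7%. The bias depends wholly on the assumed q, on 3 to 5 gradings per subject and on the correlation between visits. It runs from about 6% (q = 3%, correlated, 3 visits) to 41% (q = 10%, independent, 5 visits). Confirmation lowers it in every case calculated. This is a change that should be made; it does not stop the trial from running.

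**What to change.** In Protocol 14.2, the synopsis and SAP 1.3.1.1:

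1. Take the Cycle 1 Day 1 pre-dose grade, and that day's list of LM-attributed symptoms and signs, as the reference. State that this grading is pre-dose, because the visit list in Protocol 9.2.2 does not.
2. Count a subject as improved in the primary rate only if a decrease of at least 1 grade in the same symptom or sign, without worsening of the other LM-attributed symptoms or signs, is also present at the next scheduled LM assessment, end-of-treatment visit included.
3. Report the single-visit rate with its exact confidence interval as supportive.

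The cost is wording only. The grades are already collected and no visit is added. The downside is that brief improvement, or improvement first seen at the last assessment, no longer counts, and that the confirmation interval varies from about 2 weeks (Cycle 1 Day 14 to Cycle 2 Day 1) to about 8 weeks (after Cycle 3). The primary rate may therefore be lower. If it were 15% rather than 20%, the chance of at least 3 of 20 would be 60% instead of 79%, so the sample size text should say which rate the 20% describes.
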